#### Clinical Trial Protocol Including Amendments Nos. 01 to 04 BNT162-04

Page 65 of 133 Version: 10.0 Date: 12 MAY 2021

Monitoring details describing strategy (e.g., risk-based initiatives in operations and quality, such as risk management and mitigation strategies and analytical risk-based monitoring), methods, responsibilities and requirements, including handling of noncompliance issues and monitoring techniques (central, remote, or on site monitoring) are provided in the Monitoring Plan.

The sponsor or designee is responsible for the data management of this trial including quality checking of the data.

The sponsor assumes accountability for actions delegated to other parties (e.g., CRO).

Trial monitors will perform ongoing source data verification to confirm that data entered into the CRF by authorized site personnel are accurate, complete, and verifiable from source documents; that the safety and rights of trial subjects are being protected; and that the trial is being conducted in accordance with the currently approved protocol and any other trial agreements, GCP, and all applicable regulatory requirements.

Records and documents, including signed ICFs, pertaining to the conduct of this trial must be retained by the investigator for 30 years after trial completion unless local regulations or institutional policies require a longer retention period. No records may be destroyed during the retention period without the written approval of the sponsor. No records may be transferred to another location or party without written notification to the sponsor.

#### 10.1.8 Source documents

Source documents provide evidence for the existence of the trial subject and substantiate the integrity of the data collected. Source documents are filed in the ISF.

Data entered in the CRF that are transcribed from source documents must be consistent with the source documents or the discrepancies must be explained. The investigator may need to request previous medical records or transfer records, depending on the trial. Also, current medical records must be available.

Source data are all information in original records and certified copies of original records of clinical findings, observations, or other activities in a clinical trial necessary for the reconstruction and evaluation of the trial. Source data are contained in source documents (original records or certified copies).

Source documents are original documents, data, and records (e.g., hospital records, clinical and office charts, laboratory notes, memorandums, subject diaries or evaluation checklists, pharmacy dispensing records, recorded data from automated instruments, copies or transcriptions certified after verification as being accurate copies, microfiches, photographic negatives, microfilm or magnetic media, x-rays, subject files, and records kept at the pharmacy, at the laboratories and at medico-technical departments involved in the clinical trial).

#### 10.1.9 Trial and site start and closure

The trial start date is the date on which the trial will be open for enrollment of trial subjects.

#### Clinical Trial Protocol Including Amendments Nos. 01 to 04 BNT162-04

Page 66 of 133 Version: 10.0 Date: 12 MAY 2021

The sponsor reserves the right to close the trial site or terminate the trial at any time for any reason at the sole discretion of the sponsor. Trial sites will be closed upon trial completion. A trial site is considered closed when all required documents and trial supplies have been collected and a trial site closure visit has been performed.

The investigator may initiate trial site closure at any time, provided there is reasonable cause and sufficient notice is given in advance of the intended termination.

Reasons for the early closure of a trial site by the sponsor or investigator may include but are not limited to:

- Failure of the investigator to comply with the protocol, the requirements of the IEC or local health authorities, the sponsor's procedures, or GCP guidelines.
- Inadequate recruitment of trial subjects by the investigator.
- Discontinuation of further trial treatment development.

If the trial is prematurely terminated or suspended, the sponsor shall promptly inform the investigators, the IECs, the regulatory authorities, and any CROs used in the trial of the reason for termination or suspension, as specified by the applicable regulatory requirements. The investigator shall promptly inform the trial subject and should assure appropriate follow-up.

# 10.1.10 Publication policy

The results of this trial may be published or presented at scientific meetings. If this is foreseen, the investigator agrees to submit all manuscripts or abstracts to the sponsor before submission. This will allow the sponsor to protect proprietary information and to provide comments.

The sponsor will comply with the requirements for the publication of trial results. In accordance with standard editorial and ethical practice, the sponsor will generally support publication of multi-site trials only in their entirety and not as individual site data. In this case, a coordinating investigator will be designated by mutual agreement.

Authorship will be determined by mutual agreement and in line with International Committee of Medical Journal Editors (ICMJE) authorship requirements.

#### 10.1.11 Protocol preparation and approval

This protocol has been prepared, reviewed and approved, including wet ink sign-off by the sponsor's responsible person, in accordance with the sponsor's standard operating procedures. Documentation of this process is filed in the Trial Master File (TMF).

# 10.2 Clinical laboratory tests

Blood will be drawn and urine will be collected for clinical laboratory tests at the times given in the SoA (Section 1.3).

Page 67 of 133 Version: 10.0 Date: 12 MAY 2021

# Hematology

Hemoglobin, hematocrit, red blood cell count, white blood cell count and differential (neutrophils, lymphocytes, monocytes, eosinophils, basophils), platelet count.

## **Clinical chemistry**

Alkaline phosphatase, creatinine, ferritin, C-reactive protein, albumin, alanine aminotransferase, amylase, aspartate aminotransferase, gamma glutamyl transpeptidase, total bilirubin, blood urea nitrogen, glucose, lipase, sodium, potassium, calcium.

FSH: Only in women who are not of childbearing potential.

#### **Urinalysis**

Dipstick: glucose, bilirubin, ketone, specific gravity (1 mL  $\triangleq$  1 g), blood, pH, protein, urobilinogen, nitrite, and leukocytes.

Microscopic urinalysis: If warranted by dipstick results, urine sediment will be microscopically examined for presence of red blood cells, white blood cells, casts, crystals, epithelial cells, and bacteria.

# 10.3 Adverse events: Definitions and procedures for recording, evaluating, follow-up, and reporting

#### 10.3.1 Definition of AE and TEAE

- An AE is any untoward medical occurrence in a clinical study participant, temporally associated with the use of study intervention, whether or not considered related to the study intervention.
  - NOTE: An AE can therefore be any unfavorable and unintended sign (including an abnormal laboratory finding that **is clinically significant**), symptom, or disease (new or exacerbated) temporally associated with the use of study intervention.
- Events after signing ICF and before IMP administration will be handled as AEs.
- A TEAE is defined as any AE with an onset date on or after the first administration
  of IMP (if the AE was absent before the first administration of IMP) or worsened
  after the first administration of IMP (if the AE was present before the first
  administration of IMP). AEs with an onset date more than 28 d after the last
  administration of IMP will be considered as treatment emergent only if assessed as
  related to IMP by the investigator.

## 10.3.1.1 Events meeting the AE definition

Any abnormal laboratory test results (hematology, clinical chemistry, or urinalysis)
or other safety assessments (e.g., ECG, radiological scans, vital signs
measurements), including those that worsen from baseline, and which are
considered clinically significant in the medical and scientific judgment of the
investigator, may be considered as AEs.

#### Clinical Trial Protocol Including Amendments Nos. 01 to 04 BNT162-04

Page 68 of 133 Version: 10.0 Date: 12 MAY 2021

- Reactogenicity need only be reported as an AE if doing so provides clinically significant information not available elsewhere (such as the solicited reactions listings), e.g., severe reactogenicity lasting longer than the period of solicitation of symptoms in the subject diary. Diagnostic AEs for local and/or systemic reactogenicity, e.g., "injection site reaction" or "flu-like illness", should generally be preferred over AEs reporting of individual signs and symptoms.
- New conditions or (at the discretion of the investigator) any worsening of a preexisting condition detected or diagnosed after Visit 0.
- Signs, symptoms, or the clinical sequelae of a suspected drug-drug interaction.
- Signs, symptoms, or the clinical sequelae of a suspected overdose of either trial treatment or a concomitant medication. Overdose per se will not be reported as an AE/SAE.

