# 6.6.1 Dose limiting toxicity

During the time of enrollment into a given dose escalation cohort in Part A, if any of the following events occur, it will be considered an individual dose limiting toxicity and further dosing in that cohort will be stopped:

- Anaphylactic reaction considered related.
- Generalized urticaria considered related.
- Four trial subjects in that cohort with any severe unsolicited local event, if considered related and not manageable with simple measures (e.g., cooling, analgesia, nonsteroidal anti-inflammatory drugs [NSAIDs]).
- AEs within 7 days of vaccination assessed by the investigator to be potentially lifethreatening (Grade 4) and that are possibly related, or for which there is no alternative, plausible, attributable cause.
- Any systemic SAE within 7 days of vaccination that is assessed by the investigator as possibly related, or for which there is no alternative, plausible, attributable cause.
- Any fever >40.0°C (>104.0°F) within 7 days of vaccination considered related and confirmed by an investigator or medically qualified person.
- Two trial subjects (at any dose level) with the same or similar severe (Grade 3 or higher) AE or reactogenicity (including clinically significant laboratory abnormalities) within 7 days of vaccination, considered related, or for which there is no alternative, plausible, attributable cause (for severity grading of AEs see Section 10.3.1.7).

Approval from the SRC will be required prior to any further dosing in the affected cohort. The SRC may call for the opening of a lower dose level cohort.

The same events will prompt IMP discontinuation for individual subjects as described in Section 6.6.4. Tasks connected to the discontinuation of IMP are described in Section 7.1.

The above guidance regulates how potential dose limiting toxicities may influence the decisions to further enroll trial subjects in any cohort. These decisions are taken by the SRC based on the 48 h safety data from the first 6 subjects of each cohort (see Section 4.1). Due to the staggered sentinel dosing design, subjects will have been followed for 4 d for the sentinel subjects when this SRC decision is made.

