#### 8.3.3 Follow-up of AEs and SAEs

After the initial AE/SAE report, the investigator is required to proactively follow each trial subject at subsequent visits/contacts. All AEs/SAEs/dose limiting toxicities (DLTs) will be followed until resolution, stabilization, the event is otherwise explained, or the trial subject is lost to follow-up (as defined in Section 7.3). Further information on follow-up procedures is provided in Section 10.3.1.7.

The investigator is obligated to perform or arrange for the conduct of supplemental measurements and/or evaluations as medically indicated or as requested by the sponsor to elucidate the nature and/or causality of the AE or SAE as fully as possible. This may include additional laboratory tests or investigations, histopathological examinations, or consultation with other healthcare professionals.

New or updated information will be recorded in the originally completed CRF.

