- Related TEAE
- Grade >=3 TEAE
- Related grade >= 3 TEAE

EudraCT No: 2020-003267-26

- TEAEs with dose limiting toxicity (DLT)
- Any treatment emergent serious adverse event (TESAE)
- Related TESAE
- Deaths

Overall summary of TEAEs

The number and percentage of subjects reporting at least one TEAE and the number of TEAEs will be summarized for all TEAE types defined above for each defined time interval.

The same analysis will be done for treatment emergent AESIs (TEAESIs) by time intervals.

The same analysis will be done excluding TEAEs which fulfil the following criteria:

- Are based on solicited reporting via subjects' diaries (all preferred terms included in 'BNT162-01 AEs based on solicited reporting via subjects diaries v3.0') and
- For prime or boost immunization, respectively, has a start and end date in the time period between dosing and
 - 1) the day of last diary entry (inclusive) or
 - 2) day 7 after dosing (inclusive)

whatever comes first.

TEAEs with missing start or end date will remain included.

For each defined time interval, the number and percentage of subjects reporting at least one TEAE will be summarized by PT nested within SOC for each of the following AE types:

Any TEAE, Related TEAE, Grade >=3 TEAE, Related grade >=3 TEAE, Any TESAE, Related TESAE, TEAEs with unresolved, fatal or unknown outcome, and any TEAE but excluding TEAEs which are based on solicited reporting via diaries as defined for the overall summary. If a SOC / PT is reported more than once for a subject, the subject will only be counted once for this SOC / PT. All TEAE summary tables will be sorted alphabetically by SOC and PT within SOC.

TEAE by grade

The number and percentage of subjects with TEAEs will be summarized by worst grade by PT nested within SOC by time interval. The worst grade will be counted if a TEAE is reported more than once by the same subject for this SOC / PT in one time interval.

AE listings

All AEs, AEs with DLT, AEs of subjects who discontinued early due to an AE and SAEs will be listed.

TEAE figures

The most frequent TEAEs excluding TEAEs which are based on solicited reporting via diaries will be presented graphically using a bar plot by time interval.

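### The SAP draws its DLT table and listing only from AE records, but two of the seven DLT criteria can be met by solicited reactions that the protocol does not require to be recorded as AEs

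*Protocol*

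**What the plan says.** **DLT criteria (Protocol 6.6.1).** Seven are listed. Two can be met by a solicited reaction:
- First, the fever criterion: "Any fever >40.0°C (>104.0°F) within 7 days of vaccination considered related and confirmed by an investigator or medically qualified person".
- Second, the two-subject criterion: "Two trial subjects (at any dose level) with the same or similar severe (Grade 3 or higher) AE or reactogenicity", within 7 days of vaccination, and either related or without another plausible cause.

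The Grade 4 criterion, by contrast, is worded for AEs only: "AEs within 7 days of vaccination assessed by the investigator to be potentially lifethreatening (Grade 4".

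**Recording rule (Protocol 10.3.1.1).** "Reactogenicity need only be reported as an AE if doing so provides clinically significant information not available elsewhere (such as the solicited reactions listings". The one example given is severe reactogenicity that lasts beyond the diary solicitation period.

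**DLT capture (Protocol 6.6.1 and 10.3.1.10).** Each DLT is entered in the CRF and reported to the sponsor on the SAE form within 24 hours, even if it is not serious. The CRF page is not named, and nothing states that the entry is an AE record.

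**DLT output (SAP 6.4.3).** The table is one of the TEAE types, "TEAEs with dose limiting toxicity (DLT". The listing is described thus: "All AEs, AEs with DLT, AEs of subjects who discontinued early due to an AE and SAEs will be listed".

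**Reaction output (SAP 6.4.1, 6.4.2 and Appendix 1).** Solicited reactions are tabulated by type and worst grade per interval, and are listed. DLT status is not mentioned. The separate Grade 3 or higher reaction summary planned in the protocol has been dropped.

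**The concern.** The second of these criteria sets reactogenicity beside AE as an alternative, so the protocol foresees a DLT that is a reaction rather than an AE. The recording rule then allows a severe reaction inside the 7-day diary window to stay out of the AE data, because it is already in the solicited listings. The SAP looks for DLTs only in the AE data. Each rule is reasonable alone; together they leave a route by which a DLT is never tabulated as one.

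What is at stake is the faithfulness of a safety output. In a dose-escalation trial, readers will take the DLT table as the record of which cohorts met a stopping criterion. If it is incomplete, it can show none at a dose where the SRC dealt with one, and the worst-grade tables would not reveal the difference.

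**Working it through.** **1. The plan's own figure.** Protocol 9.2 and SAP 4 give the chance of seeing an event of 15% incidence at least once in 12 subjects: 1 − 0.85^12 = 1 − 0.1422 = 0.8578, which matches the stated 85.8%. The point does not depend on it.

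**2. Criteria open to solicited reactions.** Of the seven, fever and the two-subject criterion qualify: 2 of 7. Neither is met by a diary entry alone. Both need a relatedness assessment (for the two-subject criterion, absence of another plausible cause also suffices), and the fever must be confirmed by an investigator or medically qualified person.

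**3. Path of one such DLT.** Take two subjects with the same Grade 3 reaction on day 2, considered related.

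| Place | Is it there? | Source |
|---|---|---|
| Diary and solicited-reaction data | Yes | Protocol 8.2.8 |
| CRF, as a DLT | Yes, page not named | Protocol 6.6.1 |
| SAE form to sponsor | Yes | Protocol 6.6.1, 10.3.1.10 |
| AE record | Not required | Protocol 10.3.1.1 |
| SAP worst-grade tables and reaction listings | Yes, without DLT label | SAP 6.4.1, 6.4.2 |
| SAP DLT table and listing | Only if there is an AE record | SAP 6.4.3 |

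No section adds a second source to the last row.

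**4. Is the route remote?** The documents give no Grade 3 reaction rate, so the rates p below are assumptions, with every such reaction taken as related. For one cohort of 12, P(at least 2) = 1 − (1 − p)^12 − 12p(1 − p)^11:
- p = 2%: 1 − 0.7847 − 0.1922 = 0.023
- p = 5%: 1 − 0.5404 − 0.3413 = 0.118
- p = 10%: 1 − 0.2824 − 0.3766 = 0.341
- p = 20%: 1 − 0.0687 − 0.2062 = 0.725

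The criterion is not confined to one dose level, so pooling cohorts raises these figures. They give the chance that the criterion is met in a cohort, not the chance that a DLT is left out of the output. The latter depends on how sites recorded such reactions, which the documents do not show.

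**The case against.** The case on the other side is substantial.

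- **AE recording may be triggered anyway.** The duration example in 10.3.1.1 is only an example. Relatedness, DLT status and action taken are not described as diary items, so an investigator could well decide that an AE record adds something. Protocol 10.3.1.7 also asks for clinically significant findings to be documented as AEs, and SAP 6.4.3 expects some diary-type events among the TEAEs. This stands as a reason to expect that many such reactions were recorded. It is not a rule that all must be.
- **Capture is mandatory.** CRF entry and the SAE form secure reporting to the sponsor. The SAP's wording may mean that the DLT flag sits on the AE page, but the CRF is not available to check. Neither point makes the SAP use a DLT that has no AE record.
- **The event is not lost.** Worst-grade tables and listings still show it. Subjects without a boost are outside the Safety Boost Set and are listed with a reason under SAP 6.2; exposure is listed under SAP 6.7.1. This stands: what may be missing is the DLT label and count.
- **Decisions did not use the table.** The SRC acted on 48-hour safety data, and there is no DLT-rate rule or hypothesis test. This stands and limits the severity.

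A reader might also infer from Protocol 8.3.3 ("All AEs/SAEs/dose limiting toxicities (DLTs) will be followed until resolution") that DLTs are a category apart from AEs. That does not follow. The same list names SAEs separately, although Protocol 10.3.1.4 says that only an AE can be an SAE, so the listed categories overlap.

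**Conclusion.** The gap is real, but it is a gap in specification and not a demonstrated loss. Following the stated rules, a DLT met by reactogenicity can be absent from the SAP's DLT table and listing. This rests on reading 10.3.1.1 as not obliging an AE record for a severe reaction within the diary period, and on the SAP drawing DLTs only from TEAE and AE records, as its labels say.

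Two stronger readings are not supported. A reader might infer that diary entries by themselves create DLTs; both criteria need an investigator-side assessment, and fever also needs medical confirmation. A reader might take 12%, 34% or 73% (assumed rates of 5%, 10% and 20%) as the risk that DLTs go missing; those figures show only that the two-subject criterion is not a remote event. The probability of omission cannot be derived from the documents, and it could be zero if sites recorded every such reaction as an AE.

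Severity is minor to moderate. No sample size, hypothesis or primary endpoint changes, but a safety table could be incomplete.

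**What to change.** **SAP 6.4.3 (main change).** Define the DLT table and listing as all subjects with an event meeting a Protocol 6.6.1 criterion, taken from AE and solicited-reaction records together. Reconcile them with the DLT reports on the SAE form and the SRC minutes, and present them by cohort and immunization. Footnote any reaction that appears in both the AE and the solicited outputs.

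**Protocol 10.3.1.1 (secondary).** A sentence requiring any reaction that meets a 6.6.1 criterion to be recorded as an AE with a DLT flag would close the gap at source. It can no longer govern prospective recording here: the protocol states that Part A vaccinations were complete as of 12 March 2021, before protocol version 10.0 (12 May 2021) and SAP version 3.0 (27 April 2022).

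**Cost.** One SAP definition, a reconciliation against reports that the sponsor should already hold, and a footnote. If every DLT proves to have an AE record, the table is unchanged and the reconciliation documents that it is complete.

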## 10.3.1.2 Events not meeting the AE definition

- Medical or surgical procedure (e.g., endoscopy, appendectomy): the condition that leads to the procedure is the AE.
- Situations in which an untoward medical occurrence did not occur (social and/or convenience admission to a hospital).

# 10.3.1.3 Suspected adverse reaction

All untoward and unintended responses to an IMP-related to any dose administered.

- The definition also covers medication errors and uses outside what is foreseen in the protocol, including misuse and abuse of the IMP.
- The definition implies a reasonable possibility of a causal relationship between the event and the IMP. This means that there are facts (evidence) or arguments to suggest a causal relationship.

#### 10.3.1.4 Definition of SAE

If an event is not an AE per definition above, then it cannot be an SAE even if serious conditions are met (e.g., hospitalization for signs/symptoms of the disease under trial, death due to progression of disease).

An SAE is defined as any untoward medical occurrence that, at any dose:

- Results in death
- Is life-threatening

The term "life-threatening" in the definition of "serious" refers to an event in which the trial subject was at risk of death at the time of the event. It does not refer to an event which hypothetically might have caused death if it were more severe.

Page 69 of 133

Version: 10.0

Date: 12 MAY 2021

- Requires trial subject hospitalization or prolongation of existing hospitalization
  - In general, hospitalization signifies that the trial subject has been detained (usually involving at least an overnight stay) at the hospital or emergency ward for observation and/or treatment that would not have been appropriate in the physician's office or out trial subject setting. Complications that occur during hospitalization are AEs. If a complication prolongs hospitalization or fulfills any other serious criteria, the event is serious. When in doubt as to whether "hospitalization" occurred or was necessary, the AE should be considered serious.
- Results in persistent disability/incapacity:
  - This definition is not intended to include experiences of relatively minor medical significance such as uncomplicated headache, nausea, vomiting, diarrhea, influenza, and accidental trauma (e.g., sprained ankle) which may interfere with or prevent everyday life functions but do not constitute a substantial disruption.
- Is a congenital anomaly or a birth defect.
- Other situations:
  - Medical or scientific judgment should be exercised in deciding whether SAE reporting is appropriate in other situations such as important medical events that may not be immediately life-threatening or result in death or hospitalization but may jeopardize the trial subject or may require medical or surgical treatment to prevent one of the other outcomes listed in the above definition. These events should usually be considered serious.

